Appendix III - Khorana Score

Appendix IV - Non CTCAE Bleeding Grading Scale

Appendix V - Phone Contact Sheet

Appendix VI - Patient Instructions

Appendix VII - Patient Compliance Information

Schema

Unacceptable adverse events or patient refusal at any time → Off Study

1 Cycle = 30 days

Generic name: Apixaban
Brand name(s): Eliquis®
Availability: Biologics, Inc.

1.0 Background

1.1 Treatment

Active cancer is associated with a markedly increased risk of both incident and recurrent venous thromboembolism. The rate of recurrence has been estimated to be between 2 to 9 fold higher compared to patients without cancer (1-8). For those cancer patients who suffer a VTE recurrence, the risk of death is increased 3-fold particularly if the recurrent event is a pulmonary embolism (9). In keeping with these data, current guidelines recommend continued anticoagulation therapy beyond the acute treatment phase of 3 – 6 months until there is no longer evidence of active cancer (10). This recommendation distinguishes primary treatment (first 3 – 6 months following VTE confirmation) from secondary prevention which includes continued treatment beyond 6 months. These guideline recommendations however are based on scant data with an evidence grade limited to expert opinion only (Grade 2C)(10). Of note, patients with cancer also carry an increased risk of anticoagulant associated major bleeding (2, 5, 11-14). Balancing the risk of VTE recurrence with the risk of anticoagulant associated major bleeding complicates decision making for these patients. Prolonged anticoagulant therapy may not be beneficial for all cancer patients and may indeed provoke harm in some. In the end, there are limited data to inform decision making for these patients beyond 6 months of therapy.

The LITE investigators randomized 200 cancer patients to receive warfarin or low molecular weight heparin (tinzaparin) for 3 months for the acute treatment of VTE (15). Thereafter, patients were assessed for an additional 9 months following anticoagulation discontinuation. At three months, 6% of those patients randomized to tinzaparin compared to 10% on warfarin suffered an acute VTE recurrence which did not differ significantly between treatment allocations. At 12 months, an additional 7% of patients in the tinzaparin group (total of 13%) compared to an additional 16% in the warfarin arm (total of 26%) suffered VTE recurrence ($p=0.044$; risk ratio 0.44; absolute difference 9.0%, (95% CI -21.7% to -0.7%)). Major bleeding events were 7% for both groups at 3 months. Death occurred in 20% for both groups at 3 months and 47% of both groups at 12 months. The high rate of VTE recurrence and death can be appreciated following anticoagulation discontinuation.

The DACUS trial assessed cancer patients with first episode of DVT who had been treated with low molecular weight heparin (LMWH) for 6 months (16). After 6 months, patients underwent duplex ultrasound imaging to assess residual DVT. Those with residual thrombus were then randomly assigned to continue LMWH for an additional 6 months or to discontinue therapy. For those patients with thrombus resolution (no residual thrombus), anticoagulation was discontinued. They enrolled 347 patients of whom 242 patients had residual DVT. Of these, recurrence occurred in 22 of the 119 patients (18%) with continued LMWH compared to 27 of 123 patients (22%) who stopped therapy. For those patients without residual thrombus, the recurrence rate was low at 2.9% (3/105 patients). This study suggests that continued anticoagulant therapy beyond 6 months based on ultrasound evidence of residual thrombus provides only a modest reduction in recurrent venous thromboembolism. As such, this study does not support current guidelines for extending secondary prevention with prolonged LMWH therapy beyond 6 months. Furthermore, decisions based on the presence of residual thrombus after acute therapy has not been deemed sufficiently well validated to receive guideline endorsement. Moreover, this information is not sufficient to meet clinical

equipoise when considering a randomized trial design in cancer patients. For patients with active cancer who have completed 6 month of anticoagulants, there would be little appetite for a randomized trial where one group might be randomized to placebo given the high rate of VTE recurrence in these patients.

Guideline recommendations for patients with VTE in the setting of an active malignancy include extended anticoagulation with LMWH as the preferred anticoagulant regardless of the bleeding risk (10). Anticoagulants are often continued until there is no evidence of active malignancy defined as any evidence of cancer on cross-sectional imaging or any cancer related treatment (surgery, radiation, or chemotherapy) within the past 6 months. Chronic LMWH therapy however has several disadvantages. First, LMWH is given by subcutaneous injections which may be painful and cause considerable local ecchymoses and hematomas. Second, the cost of LMWH may be prohibitive. For individuals without insurance, this can be more than \$100 USD daily. Because this treatment is often given for months on end, health-care costs for medications alone can be thousands of dollars. Third, thrombocytopenia associated with the cancer or cancer treatments limit its use and raise clinical concerns regarding possible heparin induced thrombocytopenia. Fourth, there is neither a specific nor effective proven antidote should the patient develop bleeding complications. Fifth, renal failure which can be common with cancer or cancer related treatment limits the use of this medication. For these combined reasons, an alternative anticoagulation therapy for patients with cancer associated VTE would be extremely attractive.

1.2 Investigational Agent

Apixaban (Eliquis) is an oral direct factor Xa inhibitor which impairs coagulation by inhibiting the conversion of prothrombin to thrombin. It does not require antithrombin for antithrombotic activity and inhibits both free and clot-bound FXa. Apixaban has a half-life of about 12 hours and thus is dosed twice-daily. Bioavailability is approximately 50% after oral dosing with maximum concentrations at 4 hours post ingestion. The pharmacokinetics are linear and plasma protein binding in humans is high at approximately 87% with a volume of distribution of approximately 21 liters. Apixaban is metabolized in the liver mainly via the CYP3A4 pathway. Renal excretion accounts for about 27% of total clearance. Approximately 25% of the drug is eliminated in the feces. This drug is not dialyzable due to its high plasma protein binding. ("The dialysis clearance of apixaban is approximately 18 mL/min resulting in a 14% decrease in exposure due to hemodialysis compared to off-dialysis period.") Apixaban is currently FDA approved for the treatment of DVT and PE, and for the reduction in the risk of recurrent DVT and PE following initial therapy, for the prophylaxis of deep vein thrombosis (DVT), which may lead to pulmonary embolism (PE), in patients who have undergone hip or knee replacement surgery and reducing the risk of stroke/systemic embolism in the setting of non-valvular atrial fibrillation.

1.3 Clinical Data to Date

The AMPLIFY investigators randomized 5395 patients with acute VTE to either apixaban (10 mg twice daily for 7 days followed by 5 mg twice daily for 6 months) or enoxaparin/warfarin (17). The primary efficacy outcome, recurrent symptomatic VTE or death related to VTE, occurred in 2.3% in the apixaban group compared to 2.7% in the conventional-therapy group. From an efficacy standpoint, apixaban was therefore deemed non-inferior to standard anticoagulant therapy. Both major bleeding and the

composite of major plus non-major yet clinically relevant bleeding were significantly lower for patients receiving apixaban. The AMPLIFY-EXT investigators randomized 2482 patients with VTE who had recently completed 6 – 12 months of anticoagulation to receive one of two doses of apixaban (5 mg twice daily or 2.5 mg twice daily) or placebo for an additional 12 months. Both apixaban doses reduced recurrent VTE without increasing major bleeding compared to placebo (18).

There are now 10 studies comparing direct oral factor inhibitors with conventional anticoagulation for treatment of patients with VTE (19). A recent metaanalysis was performed to assess the safety and efficacy of direct factor inhibitors in cancer patients with VTE by combining all of the cancer patients from each study. Patients from 6 of the 10 studies were included (dabigatran 2 studies, rivaroxaban 2 studies, edoxaban 1 study, and apixaban 1 study). Combined there were 1,132 cancer patients evaluated. Based on each of the studies included, the comparator was conventional anticoagulation with heparin and warfarin. Venous thromboembolism occurred in 3.9% of patients treated with a direct factor inhibitor and 6.0% in those assigned to conventional therapy. These rates did not differ statistically. Major bleeding occurred in 3.2% of patients treated with a direct factor inhibitor and 4.2% in those assigned to conventional therapy which also did not differ. Based on these data, direct factor inhibitor therapy appears both effective and safe compared to conventional therapy in cancer patients.

Despite these trial results, apixaban is not currently recommended for cancer related VTE treatment or secondary prevention for several reasons. First, there are limited data supporting the use of apixaban in cancer patients with no trials specifically designed to evaluate its utility in cancer patients. In the AMPLIFY treatment trial, only 2.65% (143 patients) had underlying cancer as a risk factor with only 66 patients with active cancer in the apixaban arm. In the AMPLIFY Extend trial, only 42 patients with active cancer were enrolled. Indeed, the latest guideline regarding cancer associated VTE (10) recommended against the use of apixaban (or other direct oral factor inhibitors). These recommendations however were given a very weak strength (Grade 2C) given the lack of supporting data.

In the AMPLIFY Extend trial, the comparator was placebo. This would not likely be embraced or even ethical in cancer patients with a VTE history for several reasons. First, opinion leaders in the field often recommend against the use of factor Xa inhibitors in cancer patients with VTE (personal communication). Second, many of our patients are concerned about starting a novel anticoagulant for cancer associated VTE treatment in the absence of data (personal experience). Irrespective of this knowledge limitation, the hypothesis supporting the use of apixaban in cancer related VTE management remains quite attractive. A current ACCRU trial is investigating the worth of apixaban vs LMWH for the treatment of clots in cancer patients, for 6 months.

In order to gain guideline endorsement for prolonged secondary prevention, apixaban must be assessed in a randomized controlled trial setting. The current standard of care for these patients is continued LMWH for cancer associated VTE. The guidelines favor extended anticoagulant therapy with no scheduled stop date over shorter predetermined durations irrespective of the bleeding risk.

1.4 Dose Rationale and Risk/Benefits for an Extended Period in Cancer Patients

The AMPLIFY-EXT investigators compared apixaban 5 mg twice daily or 2.5 mg twice daily to placebo in 2486 patients who had completed 6 to 12 months of anticoagulant therapy for whom there was clinical equipoise regarding continuation or cessation of anticoagulant therapy (18). The vast majority of these patients had no history of active cancer. At 12 months of follow up, recurrent VTE occurred in 1.7% of patients randomized to apixaban 2.5 mg and 1.7% for those patients randomized to apixaban 5 mg twice daily. This compared to 8.8% in the placebo arm meeting the criteria for superiority for both doses. The use of apixaban 2.5 mg was associated with a 7.2% absolute reduction of VTE recurrence (95% CI, 5.0 to 9.3; P<0.001). The 5 mg dose was associated with a 7% absolute risk reduction (95% CI, 4.9 to 9.1; P<0.001). Major bleeding was infrequent and did not differ between treatment groups: apixaban 2.5 mg (0.2%), 5 mg (0.1%) and placebo groups (0.5%). Clinically relevant non-major bleeding likewise did not differ between groups: 2.3% (placebo), 3.0% (apixaban 2.5 mg) and 4.2% (apixaban 5 mg). Based on these data, both apixaban 2.5 mg or 5 mg twice daily are attractive for extended “secondary prevention” for patients without cancer associated VTE. We hypothesize that apixaban will provide safe and effective secondary prevention for patients with cancer associated VTE who have completed 6 months (but no more than 12 months) of anticoagulant therapy.

1.5 General Design

This is a multicenter, randomized, double blind, superiority trial for safety. Participating centers will be from the Academic and Community Cancer Research United (ACCRU) research consortium. This research consortium is comprised of more than 80 leading academic institutions and community oncology practices in the United States and Canada. The goal of this consortium is to collaborate with industry partners to develop and conduct clinical trials in cancer research.

Subjects will be screened at both outpatient clinic visit appointments and during hospitalizations using direct referrals or by daily automated screening of the electronic medical record. Interested qualified subjects will be consented and offered participation in this trial. Subjects will be considered for trial participation if they have evidence of active cancer and have a history of a documented venous thrombotic event for which they have received at least 6 months (but not more than 12 months) of anticoagulant therapy. Both the date and location of the original thrombosis will be recorded, as well as the anticoagulant used for the original treatment. After randomization, patients will be allocated to receive either apixaban 5 mg twice daily or 2.5 mg twice daily. Allocation to treatment will be done centrally. Once consent has been obtained, baseline laboratory values will be established and subjects will begin treatment and follow-up for 12 months.

The principal safety outcome will be a combined endpoint of major bleeding plus clinically relevant non-major bleeding. All episodes of major bleeding, clinically relevant non-major bleeding and deaths will be evaluated by a central, blinded, independent adjudication committee. Adjudication results will be the basis for the final analyses. An independent data and safety monitoring board (DSMB) will monitor the patients’ safety and give recommendations to the executive committee.

2.0 Goals

2.1 Primary Safety Endpoint

2.11 The primary safety endpoint will include the combined endpoint: any episode of major bleeding including fatal bleeding or clinically relevant non major bleeding. In particular, we will consider the proportion of patients who experience at least one such bleeding event within 12 months of beginning treatment. The following criteria will be used to confirm and categorize a bleeding episode:

- Major bleeding is defined as overt bleeding plus a hemoglobin decrease of ≥ 2 g/dL or transfusion of ≥ 2 units of packed red blood cells, or intracranial, intraspinal/epidural, intraocular, retroperitoneal, pericardial, intra-articular, intramuscular with compartment syndrome or fatal bleeding. Intracranial hemorrhage includes intracerebral (hemorrhagic stroke), subarachnoid, and subdural bleeds (21).
- Clinically relevant non-major bleeding is defined as overt bleeding not meeting the criteria for major bleeding but associated with medical intervention, an unscheduled contact with a member of the health care team, or temporary cessation of study treatment.
- Minor bleeding is defined as overt bleeding that did not meet criteria for major bleeding or clinically relevant non-major bleeding.

2.2 Secondary Safety Endpoint

2.21 The secondary safety endpoint will be the same as the primary safety endpoint, but in this case we will consider the proportion of patients who experienced at least one such bleeding event within 6 months of beginning treatment, as this was the primary endpoint in previous studies.

2.3 Secondary Efficacy Endpoint

2.31 The secondary efficacy endpoint of this study will be VTE recurrence including DVT, PE, fatal PE, or arterial thromboembolism. The following criteria will be used to confirm and categorize a VTE recurrence:

- Suspected (recurrent) DVT: The original DVT must be confirmed by duplex ultrasonography, venography, CT, or MRI. A recurrent DVT must be distinguished from the original thrombus by comparing serial imaging modalities. In order to be classified as a recurrent event, there must be new filling defects evident on the second study not appreciated on the original images or an interval study clearly showing thrombus resolution.
- Suspected (recurrent) PE: The original PE must be confirmed by CT, MR, conventional pulmonary angiography, or VQ perfusion imaging. A recurrent PE must be distinguished from the original thrombus by comparing serial imaging modalities. In order to be classified as a recurrent event, there must be new filling defects evident on the second study not appreciated on the original images or an interval study clearly showing thrombus resolution.

- Fatal PE: PE based on objective diagnostic testing, autopsy, or death which cannot be attributed to a documented cause and for which PE/DVT cannot be ruled out (unexplained death).
- Incidental VTE recurrence: Due to the nature of cancer surveillance related imaging, it is anticipated that recurrent venous thrombosis or thrombus propagation may be identified. In order to be classified as an event, the thrombus in question must be distinguished from the original thrombus by comparing serial imaging modalities. In order to be classified as a recurrent event, there must be new filling defects evident on the second study not appreciated on the original images or an interval study clearly showing thrombus resolution.
- Arterial thromboembolism: Myocardial infarction (MI), stroke, transient ischemic attack (TIA), or peripheral arterial embolism.

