3.0 Patient Eligibility

3.1 Inclusion Criteria

3.11 Age \geq 18 years.

3.12 Confirmed acute index (original venous thrombotic) event: lower extremity or upper extremity (jugular, innominate, subclavian, axillary, brachial) DVT, PE, splanchnic (hepatic, portal, splenic, mesenteric, renal, gonadal), or cerebral vein thrombosis for which the patient has received \geq 180 days (but \leq 365 days) of anticoagulant therapy prior to registration. The date, imaging modality, and location of index event will be required. The date of initiation and specific type of anticoagulants used will also be required.

3.13 Active cancer defined as metastatic disease and/or any evidence of cancer on cross-sectional or PET imaging, cancer related surgery, chemotherapy or radiation therapy within the past 6 months. Note: non-melanoma skin cancer does not meet the cancer requirement.

3.14 Life expectancy \geq 6 months.

3.15 ECOG Performance Status (PS) of 0, 1, or 2. (Form is available on the ACCRU web site
[REDACTED]

3.16 The following laboratory values obtained \leq 30 days prior to registration.

- Hemoglobin \geq 8 g/dL
- Platelet count \geq 50,000/mm³
- Alanine aminotransferase (ALT) or Aspartate transaminase (AST) \leq 3 x ULN
- Calculated creatinine clearance must be \geq 30 ml/min using the Cockcroft-Gault formula below:

Cockcroft-Gault Equation:

$$\text{Creatinine clearance for males} = \frac{(140 - \text{age})(\text{weight in kg})}{(72)(\text{serum creatinine in mg/dL})}$$

$$\text{Creatinine clearance for females} = \frac{(140 - \text{age})(\text{weight in kg})}{(72)(\text{serum creatinine in mg/dL})} * (0.85)$$

3.17 Negative serum or urine pregnancy test done \leq 7 days prior to registration, for women of childbearing potential only.
 Note: A woman of childbearing potential (WOCBP) is defined as any female who has experienced menarche and who has not undergone surgical sterilization (hysterectomy or bilateral oophorectomy) and is not postmenopausal. Menopause is defined as 12 months of amenorrhea in a woman over age 45 years in the absence of other biological or physiological causes.

3.18 Ability to provide informed written consent.

3.19 Willing to undergo monthly follow-up assessment, either in person at the enrolling institution or by telephone (script in Appendix V).

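### The recurrent-VTE definition names no comparator image near randomization, so thrombus that formed or spread unnoticed before study entry can be counted as an on-study recurrence

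*Combined protocol and SAP*

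**What the plan says.** **Definition.** Section 2.31 applies one sentence to recurrent DVT, recurrent PE and incidental VTE: "there must be new filling defects evident on the second study not appreciated on the original images". The sentence then adds an alternative, an interval study on which the clot had clearly cleared. Each bullet also sets a prior condition. For DVT it reads "A recurrent DVT must be distinguished from the original thrombus by comparing serial imaging modalities", and the PE and incidental bullets have the equivalent.

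**Modalities.** For the index DVT, "The original DVT must be confirmed by duplex ultrasonography, venography, CT, or MRI". For the index PE the accepted methods include "conventional pulmonary angiography, or VQ perfusion imaging". No separate recurrence criterion is given for duplex or VQ.

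**Incidental findings.** Because patients have cancer-surveillance scans, "it is anticipated that recurrent venous thrombosis or thrombus propagation may be identified". These count if they meet the same rule.

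**Timing.** Inclusion 3.12 requires 180 to 365 days of anticoagulation before registration and says of the baseline record: "The date, imaging modality, and location of index event will be required". Section 6.14 allows up to 30 days from registration to first dose. The test schedule in 4.0 has no imaging row, and 7.11 calls for imaging only when recurrence is suspected.

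**Safeguards.** Exclusion 3.27 removes patients with a documented VTE during therapeutic anticoagulation. Section 1.5 lists bleeding and deaths for central blinded adjudication; non-fatal VTE is not listed.

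**Use.** Section 16.23 analyses time to first DVT/PE by the method of 16.21, which estimates and tests the difference in cumulative incidence at 6 and 12 months, one-sided at 5%. Under 8.1 and 13.5 a patient with a recurrence leaves the study, and data are entered only up to that event.

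**The concern.** An on-study recurrence should be a clot that arose after randomization. The written rule instead asks whether a clot is new since the index event, or since an interval study that is optional and undated. If anticoagulation began at about the time of the index imaging and was not interrupted, the reference image is about 180 to 395 days old at first dose (365 + 30 = 395).

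Two kinds of clot can pass the rule although they were present at randomization:

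- thrombus that formed or extended without being noticed between the index image and randomization;
- thrombus in a territory outside the original images, such as leg veins never scanned in a patient whose index event was a PE.

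Separately, filling-defect wording does not fit an index event confirmed by duplex or VQ. Whoever classifies a later CT against such a study has no stated criterion.

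VTE recurrence is the trial's only efficacy endpoint, and so its only evidence on whether the lower dose still protects. A false recurrence call also takes the patient off study and cuts short follow-up for the primary bleeding endpoint.

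**Working it through.** **1. The plan's own figure.** Section 16.1 gives about 70% power for bleeding at 18% versus 9%, 176 per arm, two-sided 5%. Formula: power = Φ[(d − z·SE0)/SE1], with SE0 = √(2·p̄(1−p̄)/n) and SE1 = √([p1(1−p1) + p2(1−p2)]/n).

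- SE0 = √(2 × 0.135 × 0.865/176) = 0.0364
- SE1 = √((0.18 × 0.82 + 0.09 × 0.91)/176) = 0.0361
- power = Φ[(0.09 − 1.96 × 0.0364)/0.0361] = Φ(0.515) = 69.7%

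This reproduces the stated figure, but it concerns bleeding. The plan states no expected rate or power for VTE recurrence.

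**2. Illustration for recurrence.** All rates here are assumed: true recurrence 7.8% (2.5 mg) and 3.9% (5 mg), plus f percentage points in each arm from clot already present at randomization. The formula is the same with n = 176 per arm. The test is one-sided 5% (z = 1.645), as 16.21 states, taken in the direction of more recurrence on 2.5 mg.

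| f | Observed rates | Risk ratio | Difference | SE0 | SE1 | Power |
|---|---|---|---|---|---|---|
| 0 | 7.8% vs 3.9% | 2.00 | 3.9 points | 0.0250 | 0.0249 | 47% |
| 2 | 9.8% vs 5.9% | 1.66 | 3.9 points | 0.0287 | 0.0286 | 39% |
| 5 | 12.8% vs 8.9% | 1.44 | 3.9 points | 0.0332 | 0.0331 | 32% |

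For f = 2: Φ[(0.039 − 1.645 × 0.0287)/0.0286] = Φ(−0.29) = 39%.

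**3. Allowing overlap.** If a share b of patients is counted because of old clot, and the rest recur at their true rate p, the observed rate is b + (1−b)p. The difference then shrinks by the factor (1−b). With assumed true rates of 10% and 5% and b = 5%, the observed rates are 14.5% and 9.75%. The risk ratio falls from 2.00 to 1.49, the difference only from 5.00 to 4.75 points, and one-sided power from 55% to 39%.

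**4. Equal true rates.** Section 1.4 gives the only recurrence rates by dose, 1.7% and 1.7%, from a mostly non-cancer trial. With p = 1.7% in both arms the risk ratio stays 1.00 and the difference 0 for any b. At b = 5% the observed rate is 0.05 + 0.95 × 0.017 = 6.6%. The 95% half-width of the difference, 1.96·√(2p(1−p)/176), grows from 2.7 to 5.2 points.

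**The case against.** The strongest reply is that the index images are not the sole reference. Serial comparison is a necessary condition, the sentence allows an interval study, and 3.27 removes known VTE on treatment. This stands in part. It means the gap concerns undetected or unimaged thrombus only. It does not close the gap: the interval study is optional, undated and limited to one showing that the clot had cleared, and no image has to be close to randomization.

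Three stronger readings are tempting, and the documents do not support them.

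- **Residual index clot is counted as recurrence, and it is common.** Section 1.1 says of the cited cancer trial: "They enrolled 347 patients of whom 242 patients had residual DVT", or 70%. That is residual index thrombus. It is not new, and it fails the requirement to be distinguished from the original clot, even where a later CT shows it more clearly than an index duplex or VQ study. The 70% is not a misclassification rate.
- **Most of the comparison window precedes randomization.** For an index event 9 months before entry and detection at 6 months, 9/(9+6) = 60%. This is a share of calendar time. It becomes a probability only with a constant hazard and silent persistence of clot, which is less plausible for events imaged because of new symptoms.
- **The efficacy comparison is biased.** The planned estimate is an incidence difference, which hardly moves. The ratio and the power change only if a true dose difference exists.

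The endpoint is also secondary and unpowered, and the primary bleeding definition is untouched. Both points stand.

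**Conclusion.** The concern holds in a limited form. As written, 2.31 can count thrombus present but unrecognized at randomization as an on-study recurrence, and its filling-defect criterion does not fit two of the modalities accepted for the index event. No listed adjudication of non-fatal VTE would catch a mistimed event.

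The size cannot be derived from the documents. If such events are unrelated to dose, which is reasonable under randomization and blinding, and if recurrence truly differs between doses, the ratio is pulled toward 1 and power is lost. In the assumed illustration the risk ratio falls from 2.00 to 1.66 or 1.44 and power from 47% to 39% or 32%, while the difference stays at 3.9 points. With equal true rates only precision suffers. Each false call also ends that patient's bleeding follow-up early. This is a worthwhile, inexpensive improvement to a secondary endpoint and no threat to the primary analysis.

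**What to change.** - **Comparator.** In 2.31, replace the reference to the original images with the most recent available pre-randomization image of that vessel territory, whether index, interval or cancer-staging. Record its date and modality beside the index data that 3.12 already requires.
- **Criterion by modality.** State what counts as new on each: a non-compressible segment on duplex, a perfusion defect on VQ, a filling defect on CT, MR or venography.
- **Analysis.** Keep every qualifying event in the main 16.23 analysis. Flag events with no comparable pre-randomization image as timing indeterminate, and repeat 16.23 without them as a sensitivity analysis only.

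The cost is protocol wording, a date and modality field if the Recurrent Thromboembolism form in 18.1 lacks one (its fields are not shown), and one extra analysis. It uses images already taken for care. The downside is that some genuine first events in a new territory will be flagged. The illustration has only about 21 true events (176 × 0.078 + 176 × 0.039 = 20.6), so the sensitivity analysis could lose noticeable precision. That is why the flagged events should stay in the main analysis.
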